The first clinical data using HepaSphere/QuadraSphere was reported by Osuga and colleagues (Osuga 2002). In this study 6 patients with large liver tumors underwent bland embolization (no doxorubicin), and 2 of them had surgery afterward. In follow up, tumors were found to have varying degrees of necrosis, from partial to complete. Histologic examination showed that the embolic occluded intratumoral vessels tightly without ischemic damage to normal tissue. Post procedural pain was minimal, and no deterioration of liver function occurred. The same author also published a larger study of 59 patients treated for hepatocellular cancer with bland HepaSphere/QuadraSphere (Osuga 2008). There were no major complications and objective response rate by mRECIST criteria was 66%, but the authors found there was a high incidence of converting patients to drug eluting chemoembolization for future treatments due to progression after bland embolization.

Two recent Phase II clinical trials have demonstrated effectiveness of HepaSphere/QuadraSphere to deliver doxorubicin in patients with hepatocellular cancer. A multisite, open label investigation in Italy (Grosso 2008) evaluated 50 patients who had a maximum of 4 hepatocellular lesions each, treated with up to 3 chemoembolizations, using a dose of 50 mg of doxorubicin or epirubicin. The objective response using mRECIST criteria at 6 months was 77%. There were no major periprocedural complications. More recently van Malenstein and colleagues presented

the initial results from a single site clinical trial in Belgium (International Liver Cancer Association, Milan, Italy, Sept 2009. Manuscript in preparation). This prospective, randomized and controlled study of 30 patients compared conventional TACE to drug eluting HepaSphere/QuadraSphere. Patients received up to 3 embolizations, with a dosage of 50-75 mg/m² of doxorubicin. Pharmacokinetic studies demonstrated a significant difference in peak and overall circulating doxorubicin between the two cohorts. The effect of the larger amount of doxorubicin in the peripheral circulation of the patients who received conventional TACE was evident in the adverse events. There were 20 grade 3 (n = 12) or grade 4 (n = 8) adverse events among the patients who received cTACE compared with no grade 4 and only 4 grade 3 events in the HepaSphere/QuadraSphere group.

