 - iii. 20% decline from any value at screening
 2. Neutropenia
 3. Alopecia
 4. Hyperpigmentation
 5. Mucositis
- iii. Evaluate Resource Utilization as assessed by:
 1. Length of stay in hospital following each TACE procedure
 2. Number of unscheduled hospitalizations
 3. Length of stay of unscheduled hospitalizations
 4. New or increased use of non-OTC pain medications
 5. New or increased use of antibiotic medications
- iv. Evaluate overall adverse event rates between the treatment groups
- v. Evaluate objective response rates as determined by mRECIST criteria in the treated area (ORR-T)
 1. In this evaluation progression is defined as new/continued tumor growth in the treated area(s) of the liver or extrahepatic spread. New

tumor growth within an area of the liver not previously treated will not be considered progression.

c. Tertiary Objectives

1. Evaluate Time to Untreatable Progression defined as hepatocellular cancer for which further localized treatment by resection, percutaneous ablation, or embolization is not an option, or when there is extrahepatic spread of the cancer

Untreatable progression will be determined by the Central Reviewers during the study treatment and protocol-specified treatment follow up visits. After the final study TACE and associated assessments, untreatable progression will be determined by the treating physician during survival surveillance

2. Explore the relationship between pharmacokinetic (PK) data and patient outcomes including survival, tumor response, and adverse events

3. Inclusion Criteria

Patients must meet all of the following inclusion criteria in order to be entered into the study:

- a. Age 18 or older
- b. Patient has signed informed consent
- c. Patient must have a diagnosis of hepatocellular cancer confirmed by at least one of the following:
 - i. Histological confirmation
 - ii. Magnetic resonance imaging (MRI) result with early enhancement and delayed enhancement washout of at least one solid liver lesion > 1 cm. Patient must also have evidence of cirrhosis or have chronic hepatitis B.
 - iii. Contrast enhanced computed tomography (CT) with early enhancement and delayed enhancement washout of at least one solid liver lesion > 1cm. Patient must also have evidence of cirrhosis or have chronic hepatitis B.
- d. Patient must not be suitable for treatment by resection or percutaneous ablation at time of study entry.

Patients not suitable for ablation due to lesion location may be enrolled

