9.1.2 Definitions

An AE is any untoward medical occurrence in a patient or clinical investigation patient and does not necessarily have to have a causal relationship with the treatment. An AE therefore can be any unfavorable or unintended sign (including an abnormal laboratory finding, for example), symptom or disease temporally associated with the use of a medicinal product or procedure, whether or not considered related to the product or procedure. A non-serious AE is any untoward medical occurrence that does not meet any of the criteria for an SAE as defined below.

Anticipated adverse events are those which typically occur due to embolization (pain, fever, fatigue, nausea, elevated liver enzymes, infection, abscess, cholecystitis, hemorrhage, thromboembolism, etc), or are drug related (alopecia, nausea, mucositis, rash, skin discoloration, myelosuppression, changes in cardiac function, etc), or are related to liver disease progression (jaundice, new tumors, biliary obstruction, metastasis, liver failure, death), or relate to pre-existing conditions. Unanticipated events are those not typically seen as a result of chemoembolization. Unanticipated adverse events must be reported to the sponsor within 24 hours of site notification of the event.

Laboratory data are to be collected as stipulated in this protocol. Clinical syndromes associated with laboratory abnormalities are to be recorded as appropriate (eg, diabetes mellitus instead of hyperglycemia).

Progression of hepatocellular carcinoma is considered an efficacy outcome parameter and should not be captured as an AE.

Patients should be instructed to report any AE that they experience to the Investigator or Study Coordinator. Patients will be assessed for AEs at each visit. AEs occurring during the clinical trial and the protocol-defined follow-up period should be recorded on the appropriate AE CRF. In order to capture the most potentially relevant safety information during this study, it is important that the Investigators record AE terms accurately and consistently throughout the study. Wherever possible, a specific disease or syndrome should be reported on the CRF rather than the associated individual signs and symptoms. If observed or reported signs or symptoms are not considered a component of a specific disease or syndrome by the Investigator, they should be recorded as separate AEs on the CRF.

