11.6.1 Adverse Events

Safety summaries will include the incidence of treatment-emergent adverse events (TEAEs). Treatment-emergent adverse events (TEAEs) are defined as any event that began on or after the date of the first embolization or worsened in severity or frequency after embolization was initiated. Events worsening in severity should be considered new adverse events. Adverse events recorded on the CRF which began prior to treatment will not be included in the summary tables but will be included in the AE data listings.

All TEAEs will be coded using the Medical Dictionary for Regulatory Activities (MedDRA) and summaries will present data for both treatment groups by System Organ Class (SOC) and Preferred Term. TEAEs will be evaluated for severity using the CTCAE when available.

All TEAE summaries will be based on the number of patients experiencing an event, not the number of AEs experienced. For example, if a patient reports the same AE on 3 separate occasions that patient will be counted only once for that preferred term. Patients reporting more than one AE in a SOC will be counted only once in the SOC total. The denominator used for calculation of the percentages will be the number of patients in the Safety population in each treatment group.

Separate summaries will be generated for the following types of TEAEs:

- Overall TEAEs
- Severe TEAEs (grade 3 or higher)
- TEAEs related to doxorubicin specifically and treatment in general
- Serious adverse events (SAEs)
- Serious adverse events related to treatment
- TEAEs resulting in death

Treatment groups will be compared on the overall adverse event rates, and the rates of doxorubicin related adverse events during the protocol specified treatment phase of the investigation using Fisher's Exact Test.

The comparison of doxorubicin related adverse events will include:

- Clinically significant decline in left ventricular ejection fraction
- Neutropenia
- Alopecia
- Hyperpigmentation
- Mucositis

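### The only test planned for overall adverse events appears to be any-grade patient incidence, probably near its ceiling; grade 3+ TEAEs and SAEs deserve a pre-specified comparison too

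*Combined protocol and SAP*

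**What the plan says.** Secondary objective iv in protocol section 2 is short: "Evaluate overall adverse event rates between the treatment groups". It sets no limit on grade, seriousness or cause.

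Section 11.6.1 carries it out: "Treatment groups will be compared on the overall adverse event rates, and the rates of doxorubicin related adverse events" are compared "during the protocol specified treatment phase of the investigation using Fisher's Exact Test". The counting unit is fixed in the same section: "All TEAE summaries will be based on the number of patients experiencing an event, not the number of AEs experienced". The section then lists separate summaries. Overall TEAEs are one entry; "Severe TEAEs (grade 3 or higher)" is another; SAEs, treatment-related SAEs and fatal TEAEs follow. No test or confidence interval is named for those severity and seriousness summaries.

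On what to expect after treatment, section 9.1.2 says: "Anticipated adverse events are those which typically occur due to embolization (pain, fever, fatigue, nausea, elevated liver enzymes, infection" and further events. It gives no frequency.

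The background (section on drug eluting chemoembolization) cites a 30-patient randomized comparison of the two treatments: "There were 20 grade 3 (n = 12) or grade 4 (n = 8) adverse events among the patients who received cTACE", against four grade 3 and no grade 4 events with the study microspheres.

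**The concern.** Fisher's exact test needs a yes/no variable per patient. Patients are the counting unit and the overall entry is listed apart from the grade 3+ entry, so the tested variable is, on its natural reading, whether a patient had any TEAE at all. A patient with one mild fever then counts the same as a patient with liver failure, and three events count the same as one.

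Such a variable loses discrimination when nearly everyone is a case. Several features of the protocol push that way:

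- common post-embolization symptoms are expected with either treatment;
- there are up to three cycles, with two embolizations per cycle in bilobar disease (section 5);
- clinically significant laboratory changes are recorded as adverse events (sections 7.3, 7.5 and 7.7), as are clinically significant examination findings (11.6.4) and abnormal ejection fraction findings (11.6.7).

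At stake is the reading of objective iv. A non-significant any-grade test could be reported as no difference in adverse events even if one arm had clearly more severe or serious ones. A severity comparison added after unblinding would be open to the charge of being post hoc.

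**Working it through.** **Inputs from the documents.** Two-sided 5% significance (11.1); 1:1 allocation (section 6); 255 randomized per arm (11.2); denominator is the Safety Population, all randomized patients with at least one TACE procedure (11.3.1), so at most 255 per arm. I use 250 per arm, an assumption that allows for a few patients never treated.

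**The plan's own figure.** There is none to reproduce: the documents give no expected adverse event rate and no power for this test. Every event rate below is therefore an assumption.

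**Method.** Exact unconditional power of the two-sided Fisher test: sum, over all pairs (x, y), of Bin(x; n, p1) × Bin(y; n, p2) for the pairs where the hypergeometric p-value is at most 0.05.

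**Step 1: any-grade incidence, n = 250 per arm.**

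| Assumed rates | Power |
|---|---|
| 98% v 96% | 18% |
| 97% v 95% | 15% |
| 99% v 97% | 24% |
| 99% v 95% | 70% |
| 98% v 90% | 97% |
| 95% v 85% | 96% |
| 90% v 80% | 86% |

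The sample size matters less than the rates. At 99% v 95%, power is 71% with 255 per arm and 55% with 196 per arm.

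**Step 2: what a given fall in event burden does to this variable.** If the number of TEAEs per patient is Poisson with mean m, the chance of at least one is 1 − exp(−m). Take a 30% lower mean in one arm:

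- m = 6 v 4.2: 99.8% v 98.5%, power 11%
- m = 5 v 3.5: 99.3% v 97.0%, power 37%
- m = 3 v 2.1: 95.0% v 87.8%, power 80%

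With a 20% lower mean, power is 1% at m = 6 and 9% at m = 5. The same relative reduction is nearly invisible or fairly visible, depending on the unknown mean.

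**Step 3: is a high share plausible?** Take the five events named first in section 9.1.2 and give each an assumed independent probability q. The chance of at least one is 1 − (1 − q)^5: 83% at q = 0.3, 92% at q = 0.4, 97% at q = 0.5. A share near the ceiling is plausible but not certain.

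**Step 4: the same test on patients with a grade 3+ TEAE, n = 250 per arm.**

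| Assumed rates | Power |
|---|---|
| 40% v 28% (30% fewer) | 79% |
| 30% v 20% (a third fewer) | 70% |
| 20% v 14% (30% fewer) | 39% |

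This variable is not always more powerful. It addresses severity directly and is not held against a ceiling at rates like these.

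**The case against.** A reader might infer that, by the protocol's own account, almost every patient in both arms will have an event, so that the test can show almost nothing. The documents do not support either half. Section 9.1.2 defines anticipated events for reporting purposes; its list also includes abscess, cholecystitis and hemorrhage, and it states no rate. The background even reports little post-procedural pain in one six-patient series of bland embolization. Steps 1 and 2 show good power once one arm falls to about 90%, or when mean event counts are near three.

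It is also fair to say that comparing any-grade gaps of 2 points with grade 3+ gaps of 10-12 points flatters the alternative. With an equal 2-point gap, grade 3+ at 40% v 38% has only 6% power. The gain in power from a grade 3+ test therefore rests on assumed rates. The cited 20 v 4 result does not settle this: it counts events, not patients, in a small trial whose arm sizes are not given.

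Severe events are not hidden or wholly untested. Section 11.6.1 requires by-arm tables of grade 3+ TEAEs and SAEs. Five doxorubicin-related events have their own Fisher comparison, which matters because the background attributes the 20 v 4 difference to circulating doxorubicin. Unscheduled hospitalizations are tested in 11.5.4.2.

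All of this stands, and it limits the point without removing it. The five named events do not include severe hepatic or embolic complications such as liver failure or hemorrhage. Hospitalization is only a partial proxy for seriousness. The overall variable remains undefined, and no inferential comparison is named for grade 3+ TEAEs or SAEs.

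**Conclusion.** The point holds as a cheap improvement to a secondary safety analysis; it does not touch the primary endpoint. On the natural reading of 11.6.1, objective iv is tested only on any-grade patient incidence, which is blind to severity, seriousness and repetition and is probably close to its ceiling.

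The size of the loss cannot be fixed from the documents. At 250 per arm, power is 15-24% for the 2-point gaps examined with both arms at 95-99%, and 70-97% once the gap is 4 to 8 points. These figures rest on assumed rates.

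The firmer part of the finding does not depend on those rates: the adverse event difference that the protocol cites between the two treatments lies in grade 3-4 events, and the plan names no between-arm comparison at that level.

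**What to change.** In section 11.6.1:

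1. State that the overall adverse event comparison is the proportion of Safety Population patients with at least one TEAE of any grade.
2. Add pre-specified between-arm comparisons, each with Fisher's exact test and a 95% confidence interval for the difference, of the proportion of patients with at least one grade 3+ TEAE and the proportion with at least one SAE.
3. Name the grade 3+ comparison as the main one for interpreting objective iv.

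The any-grade test may stay. A model for event counts per embolization is optional.

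The cost is a few lines of text, agreed before the treatment-phase database is unblinded. The summaries are already planned and no new data are needed. The small downside is two more secondary comparisons at an unadjusted 5% level.

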The inclusion criteria for the currently proposed clinical trial are in part derived from results of a Phase II multisite clinical trial of a different drug eluting embolic (DC Bead, BioCompatibles, England). That investigation (Lammer 2009) included 201 patients who received up to 3 embolizations, with a dosage of doxorubicin up to 150mg each time. The patients were randomized to receive either conventional chemoembolization or drug eluting embolization using the DC Bead product. The primary objective was objective response at 6 months using mRECIST criteria, but the study did not meet its endpoint (p=0.11). However, in the subset of patients with more advanced disease, that is, those who had ECOG performance levels of 1 (rather than 0), recurrent or bilobar disease, or were Child-Pugh B (rather than A), the difference in response between the conventional and drug eluting arms was statistically significant. It was determined that the reason for this difference was that individuals with greater underlying liver disease or generally poorer hepatic status were able to tolerate embolization better when the drug release was controlled by the embolic (Lencioni, International Liver Cancer Association, Milan, Italy, Sept 2009). With these results in mind, we have focused the inclusion criteria for this proposed study on those patients most likely to derive the greatest benefit from treatment with HepaSphere/QuadraSphere.

2. Study Objectives

The objectives of this prospective, randomized, blinded and controlled clinical trial are as follows:

a. Primary Objective

- i. Evaluate overall survival in patients treated with doxorubicin delivery by HepaSphere/QuadraSphere compared to conventional transarterial chemoembolization with doxorubicin, lipiodol, and particle PVA

b. Secondary Objectives

- i. Evaluate overall objective response rates (ORR) determined by mRECIST criteria (Llovet 2008; Lencioni 2010) of hepatocellular carcinomas treated with doxorubicin delivery by HepaSphere/QuadraSphere compared to conventional transarterial chemoembolization with doxorubicin, lipiodol, and particle PVA
- ii. Evaluate doxorubicin related adverse events in patients treated with doxorubicin delivery by HepaSphere/QuadraSphere compared to those treated with conventional chemoembolization with doxorubicin, lipiodol, and particle PVA
 1. Decline in left ventricular ejection fraction
 - i. 10% decline from screening to below 50%
 - ii. Absolute value of 45% or less

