The study will evaluate safety throughout the protocol specified treatment phase of the investigation by assessing adverse events, as well as clinically significant changes from baseline in laboratory values, findings on physical examination including vital signs, ECOG performance

status, and cardiac ejection fraction testing. Concomitant medication usage will also be assessed. Blood samples will be drawn for pharmacokinetic evaluation the morning after the first TACE procedure and at the time of the MRI and laboratory evaluations following the first TACE cycle. In addition, patients who are still hospitalized at least 6 hours following the first PK blood sample collection will have an additional PK blood sample drawn.

6. Randomization and Blinding

Randomization and blinding of treatment identification will be used to reduce potential bias during data collection and evaluation of clinical endpoints. The treatment assignments will be unblinded once all data from the protocol specified treatment phase has been entered into the clinical database, all of the necessary standard data cleaning techniques have been implemented, and the database has been locked.

Once the informed consent has been signed and the patient has met all the study entry criteria, the patient will be considered eligible for randomization. Patients will be randomized to either the cTACE or hqTACE treatment groups in a 1:1 ratio within 1 week of their first scheduled TACE. Randomization schedules will be generated using an adaptive randomization model (based on the algorithm developed by Simon and Pocock). The adaptive model will control the balance of treatment groups within each site and also take into account the following baseline factors which will be weighted based on importance: Child-Pugh Stage (A or B), ECOG performance (0 or 1) status, recurrent disease (yes or no), AFP (<400 ng/mL or ≥400 ng/mL), presence of macrovascular invasion (yes or no), and tumor location (unilobar or bilobar).

Patients will be blinded to the treatment group to which they are assigned. In order to minimize any bias in interpretation of tumor response, the Central Reviewers who assess treatment response will also be blinded to which treatment the patient is receiving. It is not possible for treating radiologists to be blinded to treatment group because the method of embolization is different for the 2 methods of TACE. The primary efficacy outcome of overall survival is unaffected by blinding.

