7.3 MRI and Laboratory evaluations following First TACE Cycle

MRIs of the liver, chest and pelvis and laboratory evaluations must be done within 4 weeks (± 1 week) of the first TACE cycle. If the patient received chemoembolization for bilobar disease, the MRIs and laboratory tests must be done within 4 weeks (± 1 week) of the embolization of the second lobe.

Laboratory evaluations will include those listed under screening, at a minimum, and results will be reviewed by the investigator and clinically significant changes from baseline will be reported as adverse events. Additionally, blood samples will be drawn for PK analysis. MRI results of the liver will be reviewed by Central Reviewers. If the patient has experienced a cardiac related adverse event, cardiac ejection fraction testing will be done.

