9.1 Non-serious Adverse Events

9.1.1 Assessments

The Investigators are responsible for monitoring the safety of patients who have been randomized in this study. All AEs considered to be related to study treatment, including doxorubicin treatment, will be followed until the event resolves. If patients receive other

anticancer therapy the follow-up for AEs will be stopped. AEs will be evaluated for severity using NCI CTCAE (Common Toxicity Criteria for Adverse Events), where applicable.

Investigators are required to document all AEs occurring during the study commencing with the date of randomization and including the protocol defined post-treatment follow-up period (21 CFR §312.64[b]), which is defined as 30 days post last MRI in this study, on the designated CRF pages. It is also important to record all AEs that result in permanent discontinuation of the study treatment, whether serious or non-serious. AEs that occur following the signature of informed consent but prior to randomization will not be captured. AEs that occur after the patient receives any anticancer therapy other than the study treatment they were randomized to receive will not be recorded as AEs.

Serious adverse events (SAEs), as defined below, must be reported to BioSphere Medical or its representative within 24 hours of knowledge of their first occurrence. SAEs that occur following the signature of the informed consent but prior to the first TACE procedure will not be reported. SAEs that occur after patients receive any anticancer therapy other than the study treatment they were randomized to will not be reported.

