11.1 General Considerations

In general, continuous variables will be summarized as n, mean, standard deviation, median, minimum, and maximum. Categorical variables will be summarized as the number and percentage of patients in each category.

Data from all investigational sites will be pooled in the analyses. Summary tables will present data for both treatment groups and overall, where appropriate. Data listings will include all data collected on the case report forms (CRFs), as well as any derived variables (study day, age, time to progression, etc.). Data collected on patients who are screen failures will not be included in any summary tables, listings, or analyses.

For each parameter, baseline is defined as the value reported prior to the first embolization. If multiple values were collected prior to the first embolization, the value closest to the date/time of the initiation of the first embolization will be used as baseline. This may include values collected earlier in the day on the date of first procedure.

Unscheduled data, such as information from unscheduled visits, repeat laboratory tests, or Investigator comments, will be included in the data listings. In general, these data will be excluded from the summary tables unless otherwise specified.

Any outliers detected during the review of the data will be investigated. If needed the data will be queried and corrected in the database prior to database lock and the generation of the final tables and listings.

All secondary analyses will be performed on a locked database after all patients have completed the protocol specified treatment phase of the investigation. The survival follow up data will continue to be entered into the clinical database for the primary analysis of overall survival and tertiary analysis of TTUP.

Analyses will be performed using SAS® (Statistical Analysis System), version 9.1 or higher.

Any treatment comparison with a 2-sided p-value less than or equal to 0.05 will be considered statistically significant.

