11.6.7 Cardiac Ejection Fraction (%)

Cardiac ejection fraction data will be collected at screening, after the second TACE, and at the final study visit for all patients. Cardiac ejection fraction testing will also be collected at additional time points during the protocol specified treatment phase of the investigation if the patient has experienced a cardiac related adverse event. Abnormal findings will be reported as adverse events. A summary table will be created summarizing the number and percent of patients having a clinically significant cardiac ejection fraction finding at each time point for each treatment group. This data will be presented in the data listings.

12 Data Safety Monitoring Board

A Data Safety Monitoring Board will be formed consisting of at least 3 individuals with expertise and experience in clinical trials, liver cancer and safety evaluations, but without direct involvement in the conduct of the study. The exact responsibilities, procedures, and guidelines used to manage the DSMB are described in a separate charter.

13 Records and Confidentiality

Each patient will be identified by study number only in the trial records. Study data will be recorded on pre-printed CRFs. Monitoring of study data recorded on the CRFs to source documents will be conducted for all patients to ensure accuracy and completeness.

14 Quality Control and Assurance

This study will be initiated and conducted under the sponsorship of BioSphere Medical, Inc., a wholly owned subsidiary of Merit Medical Inc. BioSphere Medical will supply pre-printed CRFs to all sites. Representatives of BioSphere Medical will monitor the study to verify study data, medical records, and CRF data in accordance with current ICH, GCPs and other applicable regulations and guidelines.

15 Good Clinical Practice

The study will be conducted in accordance with the International Conference on Harmonization (ICH) E6 for Good Clinical Practice (GCP): Consolidated Guidance and the appropriate regulatory requirement(s). The investigators will be thoroughly familiar with the appropriate use of the treatment procedure as described in the protocol. Essential clinical documents will be maintained to demonstrate the validity of the study and the integrity of the data collected. Master files should be established at the beginning of the study, maintained for the duration of the trial and retained according to the appropriate regulations.

16 Ethical Considerations

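### LVEF decline and neutropenia are measured on schedule, but the tested comparison counts investigator-reported adverse events, so a reporting difference could create or hide a difference between arms

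*Combined protocol and SAP*

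**What the plan says.** **LVEF.** Protocol Section 2 (secondary objective ii.1) lists three criteria: "10% decline from screening to below 50" per cent, a value of 45% or lower, and "20% decline from any value at screening". Ejection fraction is tested in all patients at screening (7.1), after the second cycle (7.5) and at the final visit (7.8). Extra tests after cycles 1 and 3 depend on a cardiac adverse event having occurred (7.3, 7.7). Section 11.6.1 lists the item for comparison as "Clinically significant decline in left ventricular ejection fraction". Section 11.6.7 says "Abnormal findings will be reported as adverse events" and then tabulates clinically significant findings. Neither section cites the Section 2 criteria.

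**Neutropenia.** The neutrophil count is part of the scheduled blood count (7.1, carried forward to 7.3, 7.5 and 7.7, and listed again in 7.8). For laboratory tests after each cycle, "results will be reviewed by the investigator and clinically significant changes from baseline will be reported as adverse events". No cut-off or grade defines neutropenia. CTCAE appears only for grading the severity of events already reported (9.1.1, 11.6.1).

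**Blinding.** Section 6 blinds patients and Central Reviewers, and adds: "It is not possible for treating radiologists to be blinded to treatment group".

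**Timing.** Section 9.1.1 collects adverse events to the end of the follow-up period, "which is defined as 30 days post last MRI in this study". Section 7.8 places the final visit 4 weeks, plus or minus 1 week, after the final MRI.

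**The concern.** Lower doxorubicin toxicity is the main safety argument for the device. The protocol's background on drug-eluting chemoembolization reports less circulating drug and fewer grade 3 and 4 events than with conventional TACE. Section 11.6.1 tests that argument with Fisher's exact test on reported events.

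Two of the five components, LVEF decline and neutropenia, are recorded as numbers at fixed visits in every patient. The plan nevertheless counts them only after a judgement at the site, with no written threshold in the analysis section. If sites call the same value an event more readily in one arm, the tested rates differ although the recorded values do not. A reporting gap in the opposite direction to a true effect would hide it.

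**Working it through.** The plan states no rate, power or sample size for this comparison, so there is no figure to reproduce. The check has three parts.

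**1. From measurement to counted event**

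| | Measured | Numeric rule in the protocol | What 11.6.1 counts |
|---|---|---|---|
| LVEF decline | Screening, after cycle 2, final visit, all patients | Three criteria in Section 2; unit of the 10% and 20% not stated | Adverse event described as clinically significant, no threshold cited |
| Neutropenia | Every scheduled blood count | None as an event; 1500 cells/mm³ is an entry limit (Exclusion t.ii) | Adverse event, no threshold |

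Section 11.6.2 summarises change from baseline by arm for all hematology parameters. It is descriptive, with no cut-off and no test.

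**2. What unequal reporting would do**

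Inputs from the documents: 255 randomized per arm (11.2), which is the upper limit of the safety population; two-sided 0.05 (11.1); Fisher's exact test (11.6.1). Assumed inputs: a true rate *p* equal in both arms, and reporting probabilities *r*₁ and *r*₂.

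Reported rate in arm *k* = *p* × *r*ₖ. At *p* = 20%: 0.20 × 0.90 = 18%, 0.20 × 0.80 = 16%, 0.20 × 0.70 = 14%.

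Rejection probability = Σᵢ Σⱼ Bin(i; n, p·r₁) × Bin(j; n, p·r₂) × 1[Fisher p ≤ 0.05].

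Results for n = 255 per arm:

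| True rate, both arms | 80% vs 80% | 90% vs 80% | 90% vs 70% | 90% vs 50% |
|---|---|---|---|---|
| 5% | 3.0% | 3.7% | 5.8% | 16.7% |
| 10% | 3.5% | 5.1% | 10.3% | 36.9% |
| 20% | 3.8% | 7.5% | 20.1% | 70.4% |
| 30% | 4.0% | 10.2% | 31.9% | 90.3% |

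With 196 per arm (the number before the allowance for non-evaluable patients) and a 20% true rate, the same four columns give 3.6%, 6.3%, 15.5% and 57.6%. For a rare event with a small reporting gap the effect is negligible. For a common event with a wide gap it is large.

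**3. Two details that affect the repair**

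*Unit of the LVEF criteria.* The 20% criterion adds patients only when it can be met at a value of 50 or more, because any lower value that meets it also meets the 10% criterion. If % is relative, this needs 0.8 × screening ≥ 50, so screening ≥ 62.5. If % means points, it needs screening − 20 ≥ 50, so screening ≥ 70. For example, 70 falling to 56 is 14 points, or 14/70 = 20% relative: an event under one reading and not under the other.

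*Windows.* The final visit may fall on days 28 ± 7, that is days 21 to 35 after the MRI. Adverse event collection ends at day 30. Days 31 to 35 are 5 of the 15 permitted days, and ejection fraction, neutrophil count and adverse events are all assessed at that visit.

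**The case against.** The best reply is that the LVEF endpoint is already defined. Section 11.6.1 repeats the five Section 2 items in the same order, so 'clinically significant decline' can fairly be read as shorthand for the three criteria. This stands. A reader might infer that the analysis sections abandon the Section 2 thresholds, but the documents show only a missing cross-reference and an unstated unit. Nor is there a contradiction when a fall from 52 to 49 is reported as abnormal without meeting a Section 2 criterion, since an adverse event rule may be broader than an endpoint. The reply does not help neutropenia, for which no threshold exists to refer back to.

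Three other strong readings also go too far:

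- **All investigators are unblinded.** Section 6 says so only for treating radiologists, and the plan does not say who judges laboratory or LVEF results. What remains is that no blinded assessor is named.
- **Events count only if attributed to doxorubicin.** Attribution-based summaries are a separate item in 11.6.1. For the five listed events, 'doxorubicin related' may simply be the Section 2 heading.
- **The rule on unscheduled data removes events.** Section 11.1 says "In general, these data will be excluded from the summary tables unless otherwise specified", which concerns summaries of unscheduled data. It does not take reported adverse events out of the counts, and 11.6.7 provides for extra LVEF tests.

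A fair practical objection is that scheduled blood tests about 4 weeks after each cycle can miss neutropenia between visits. Reported events therefore keep their value.

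**Conclusion.** The concern holds in a limited form. For two components with objective measurements, the tested comparison depends on site reporting: neutropenia has no threshold, and LVEF has thresholds that the analysis sections do not cite. With treating radiologists unblinded and no blinded assessor named, a reporting difference could create or hide an arm difference. The descriptive summaries in 11.6.2 would not resolve this.

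The size cannot be estimated, because the documents give no true or reporting rates. Under the assumed 20% true rate in both arms at 255 per arm, false rejection moves from about 4% to 7.5% or 20% for reporting gaps of 10 or 20 points. At a 5% true rate it stays between 3.7% and 5.8% for the same gaps. A reader might infer that the comparison is biased in favour of the device. The documents show that this is possible, but neither that it happens nor in which direction.

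The mismatch between the 30-day collection period and a final visit allowed to day 35 is a separate, smaller defect. It affects both arms. This is a secondary safety comparison, so the change is advisable rather than essential to the trial's primary conclusion.

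**What to change.** In 11.6.1 and 11.6.7:

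- Derive LVEF decline in the analysis program from scheduled post-baseline values, using the Section 2 criteria. The sponsor should state whether 10% and 20% are relative or percentage points; the documents do not settle this.
- Derive neutropenia from scheduled neutrophil counts, using a prespecified cut-off or CTCAE grade. Below 1500 cells/mm³, the entry limit, is one option.
- Compare both derived events by Fisher's exact test in the safety population.
- Use unscheduled values in a sensitivity analysis only. Extra LVEF tests are triggered by a cardiac adverse event, so including them in the main analysis would bring reporting back in.
- Keep investigator-reported rates alongside, to cover events between scheduled tests.
- State that all five listed events count regardless of attribution.

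Reconcile the adverse event period in 9.1.1 with the final-visit window in 7.8, so that findings at the final visit are counted.

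The cost is protocol and SAP wording plus a little derivation programming; the scheduled values are already collected. The downside is that asymptomatic threshold crossings will count as events.
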